If you experience an increase in your current symptoms (by 2 points on a 0-10 scale) or onset of two new symptoms of concussion while exercising at home and cannot continue, please stop for that day and try again the following day. If you experience a prolonged or severe increase of your concussion-related symptoms during exercise, then do not perform the prescribed exercises and contact your doctor.

Example Day 1 Prescribed Exercise Program

REMINDER: Note your target heart rate (page 1), wear your heart rate monitoring device, and stop exercising if your symptoms worsen.

Day 1: With Trainer

- 1: 5 Minutes Warm Up
- 2: Minimum 20 minutes at target heart rate
- 3: Minimum 20 minutes resistance training (see below)
4. 5 Minute Cool Down

Resistance Work-Out and Medications Day 1

Exercise 1: Sit Ups: 20 standard sit-ups, 3-5 sets

Modifications: 30 second plank or 20 crunches

Exercise 2: Standard Bench Press, 3-5 sets with 10 repetitions

Modifications: dumbbell chest press or push ups

Exercise 3: Dumbbell Shoulder Press, 3-5 sets with 10-12 repetitions

[figure not shown]
Modifications: Banded shoulder press or machine shoulder press

Exercise 4: Incline Dumbbell Fly, 3-5 sets with 10-12 repetitions

Modifications: incline chest press or decline push up

Exercise 5: Triceps Pushdown, 3-5 sets with 10-12 repetitions

Modifications: Triceps Dip, Bent Over Triceps Extension

Figure 3. Example SCG Program

YOUR PERSONAL STRETCHING PRESCRIPTION

Your doctor has given you a prescription for light stretching. For this research study, it is important that you follow the instructions given by your doctor below very carefully!

You will do stretching exercises each day, without doing any other type of exercise that gets your heart rate up. Your doctor has decided on a stretching routine that is safe for you, and that should not cause you to

have any concussion symptoms. If your doctor appointment is during Days 1-6 of a stretching cycle, do not do the stretches for that day. The day after your appointment, resume doing stretches.

You will be asked to tell us how you are feeling and your activity level.

Please wear your heart rate monitoring device during the exercise.

HERE IS THE PRESCRIPTION THAT YOU MUST FOLLOW

Please see the attached sheet for instructions/demonstrations of stretches that you should do each day/week. They change each day, so be sure to follow the booklet as written.

[figure not shown]
Example Day 1 Prescribed Stretching Program

Diaphragmatic breathing – Savasana

- Lie down on your back on the floor with your arms by your side, palms facing up
- Relax your legs, lay totally flat
- Breathe in deeply and slowly while counting 10
- Then breathe out deeply and slowly, counting 10, focus on pulling your stomach in
- Rest for 10 seconds

Pelvic Tilts

- Lie on floor with knees bent up
- Flatten your back to floor and hold 10 seconds (top photo below)
- Roll your pelvis the other direction and make an arch in the back hold for 10 seconds (bottom photo below)
- Rest 10 seconds and repeat 10 times

Repeat both stretches above 3 times.

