Hypothesis 1: There will be a greater reduction in the Neurobehavioral Symptoms Inventory (NSI) from pre- to post-SAET compared to the control condition. A similar finding will continue from immediate to 3 month post-SAET.

Secondary Aims:

Sub-aim 1 Cognitive Status: To determine if SAET is effective at improving cognitive impairment among SMs with persistent complaints from mTBI.

Sub-hypothesis 1: There will be a greater decrease in the Global Deficit Scores (GDS; an overall measure of cognitive impairment) post SAET in comparison to the control condition.

Sub-aim 2 Physiological Adaptation: To measure physiological adaptation associated with SAET compared to the control condition.

Sub-hypothesis 2: SAET will be associated with improved cerebrovascular blood flow regulation, as measured by Transcranial Doppler and improved cardiovascular function, as measured by changes in heart rate variability (HRV) and estimated maximal oxygen consumption (est. VO₂ max) compared to the control condition.

Sub-aim 3 Warfighter Performance: To determine if SAET participants will have improved locomotion and a higher level of occupational performance compared to the control condition.

Sub-hypothesis 3: SAET participants will have improved locomotion and physical performance (based on the Marine Corps Combat Fitness Test(CFT)) and higher ratings of occupational performance (based on supervisor ratings on the Checklist of Military Activities of Daily Living [M-ADL]) after completion of treatment and 3 months post-treatment compared to the control condition.

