9.5 Target Population

Describe the population to whom the study findings will be generalized

140 participants will be recruited for the study. Participants will be active duty service members with a history of mTBI based on the DoD diagnostic criteria (Management of Concussion/m, 2009) who have persistent elevated neurobehavioral symptoms more than 1 month from injury compared to published normative data (Soble et al., 2014). mTBI diagnosis will be confirmed through a structured clinical interview, using the Ohio State University Traumatic Brain Injury Identification Method (OSU TBI-ID) (Corrigan & Bogner, 2007), as well as through a review of participant electronic medical records (e.g., MHS GENESIS).

Participants will include male and female active duty service members who are between the ages of 18 and 55 years.

Potential service members will be recruited from the Intrepid Spirit Center at the Naval Hospital Camp Pendleton, as well as other branch clinics on Marine Corps Base Camp Pendleton. A recent report by the TBICoE Office of Surveillance identified Camp Pendleton as having the sixth most TBI encounters for active duty service members across the entire DoD, with over 400 SMs seeking treatment for a brain injury in the second quarter of 2021 alone.

Participants interested in the study will be screened for study eligibility based on inclusion/exclusion criteria dictated for this study (see details below). Individuals will be included if they report a history of at least one previous TBI, as well as elevated neurobehavioral symptoms compared to healthy SMs (Soble et al., 2014).

After screening and consent, a pre-treatment evaluation will be completed to determine baseline functioning. For each treatment, evaluations will be completed immediately post-treatment (approximately 8 weeks from baseline) and at 3 months post-treatment.

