10.0 Study Procedures, Data Management, and Privacy

10.1 Study Procedures

Describe step-by-step how the study will be conducted from beginning to end

Individuals who report interest in the study and report a history of at least one previous TBI, as well as persistent symptoms they believe to be related to that injury, will be enrolled in the study

(see **Figure 1**). Participants will complete a short screen for inclusion and exclusion criteria as dictated for this study. After screening and consenting, participants will be randomly assigned to one of two study arms, the sub-symptomatic adaptable exercise treatment (SAET) treatment group or the stretching control group (SCG) control group, and given a pre-study evaluation to capture baseline functioning. Participants will then be scheduled to begin the study intervention and will receive appointment reminders via phone, text, and/or email. For each participant, randomized to SAET or SCG, additional evaluations will be completed following their last treatment session and at 3 months post-treatment. **Figure 2** details the study procedure timeline.

Participants will be randomized into either the exercise or the stretching condition group in a 1:1 fashion within a block size of 6, which will be utilized until all potential participants are assigned to a group (70 in exercise group and 70 in stretching condition group). Halfway during recruitment, the sample size will be reassessed for balance between the two groups. If needed, adjustment of randomization, for example, to a 2:1 ratio, will be conducted but maintaining the block size of 6. Periodic adjustment may be necessary to obtain the minimum sample size for this project. The study biostatistician will conduct randomization and an assignment schedule will be provided to the project coordinator who will keep such schedule under a password-protected encryption.

Study Evaluations

Participants will undergo the following assessments and evaluations at three study time points: pre-, post-, and 3 months post-treatment.

Cognitive Assessments

Participants will undergo various neuropsychological assessments and complete self-report measures administered via paper and pencil or electronically using an approved data collection platform. Cognitive assessments will take approximately 1 hour to administer at each time point, pre-, post-, and 3 months post-treatment. Specific assessments are described below in Section 10.2.

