Exercise Habits Questionnaire: To best prescribe a personalized exercise treatment, participants will be asked to complete an exercise habits questionnaire to capture their current exercise routine and available exercise equipment to them.

Figure 1. Study Procedure Overview

[figure not shown]

Figure 2. Example of SAET Program

Your clinician has given you a prescription for light to moderate aerobic and resistance training exercise. Each week, you will be given a specific workout to complete for 5 days. Two of these days will be completed with a trainer in the clinic and three other days will be completed on your own time.

This means you will exercise each day, but you will keep your heart rate at a specific level that is lower than it would get to during regular exercise. Your doctor has decided on a heart rate that is safe for you based on the results of your exercise test.

You can perform aerobic exercise how you want (i.e. walking, jogging, stationary cycling), but it is important to avoid a lot of neck motion during exercise. Exercise should include: A short warm-up such as stretching or walking (5 minutes), a minimum of 20 minutes at the prescribed heart rate, a minimum of 20 minutes on resistance exercises provided by your trainer, and a cool-down such as stretching or walking (5 minutes).

It is very important that you only exercise according to your prescription, and that you follow the instructions given by your doctor very carefully. Even if you start to feel better while you are at home, you should not change the heart rate at which you are exercising until you have seen your doctor again. Each clinical visit, your doctor will see how you are doing and provide a new exercise prescription if you have not recovered.

For this exercise prescription, you should use the wearable device provided to you at study enrollment. Whenever you are exercising, you will wear the monitor to help you track your heart rate.

Here is your exercise prescription that you should follow until your next follow-up visit:

Your treadmill test was performed on

± 5

We would like you to exercise at a heart rate of **bpm**

When to stop?

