Neurobehavioral Symptom Inventory (NSI)	Primary Aim	The NSI is a 22 item self-report questionnaire that assesses PCS (Cicerone & Kalmar, 1995). The questionnaire is a preferred measure by the DoD and Veteran Affairs. It is well-validated in research studies on TBI and PTSD in military populations, it has known reliability and validity, as well as guidelines for assessment of change (Belanger et al., 2016; Soble et al., 2014). Test-retest reliability values ranged from .78 to .94 for the total score and from .52 to .91 for subscales (Silva, 2021).
Symbol Digit Modalities Test (SDMT)	Secondary Aim 1	Utilized to measure divided attention, visual searching and tracing, and motor speed (Smith, 2007). The test is comprised of a coding key made up of nine abstract symbols. Each symbol has a corresponding number. The test-taker is asked to visually search the key and record the number that matches each symbol as quickly as they can. The test-retest reliability is 0.80. The SDMT has good validity with other tests of attention ($r = .62-.78$). The test will be purchased from a commercial vendor, which will allow authorized use of this measure.
Paced Auditory Serial Addition Test (PASAT)	Secondary Aim 1	A serial addition task used to assess attentional processing by examining the role of immediate memory and attention (Gronwall, 1977). During administration, a series of single digit numbers are presented where the two most recent digits must be summed. The PASAT has well-studied psychometric properties with good test-test reliability and validity (Strauss et al., 2006).
Hopkins Verbal Learning Test- Revised (HVLT-R)	Secondary Aim 1	Used to assess verbal learning and memory (Brandt et al., 1998). It is a brief test with six alternate forms that can be easily administered in patients with varying cognitive disorders. The test consists of three learning trials with 12 nouns (targets) and includes a 25-minute delayed free recall trial. This measure will be purchased from a commercial vendor which will provide permission for use in the study.

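### Section 10.1 lists random assignment before the baseline evaluation and nothing in the available text withholds the arm until baseline is complete, so the self-reported NSI baseline can be collected with the arm known

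*Protocol*

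**What the plan says.** Protocol section 10.1 answers a prompt to describe the study step by step. After a short eligibility screen it continues: "After screening and consenting, participants will be randomly assigned to one of two study arms". The same sentence names the arms and ends "and given a pre-study evaluation to capture baseline functioning". The next sentence reads "Participants will then be scheduled to begin the study intervention".

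Section 9.5 also places the baseline: "After screening and consent, a pre-treatment evaluation will be completed to determine baseline functioning". It does not mention assignment.

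On control of the allocation list, section 10.1 says that the study biostatistician randomizes and that the project coordinator keeps the schedule under password protection. It does not say when a participant or an assessor learns the arm.

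On the outcome, section 10.2 states "The NSI is a 22 item self-report questionnaire", and Hypothesis 1 in section 9.3 is "There will be a greater reduction in the Neurobehavioral Symptoms Inventory (NSI) from pre- to post-SAET compared to the control condition". Section 11.6 makes change from pre-treatment to immediate post-treatment the first primary contrast. It adds an 8-point NSI change as the clinically relevant threshold.

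**The concern.** Staff who follow section 10.1 in the order written would randomize first and take the baseline second. If the arm is known by then, the participant answers a subjective symptom questionnaire knowing what treatment is coming. The arms are easy to tell apart once disclosed. One is aerobic and resistance exercise; the handout for the other says "You will do stretching exercises each day, without doing any other type of exercise that gets your heart rate up". Hope or disappointment about the arm could alter how symptoms are reported at baseline.

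That baseline feeds the first primary contrast, the 8-point definition and the secondary comparison from pre-treatment to 3 months. The primary contrast from immediate post-treatment to 3 months does not use it. Later NSI reports will be made with the arm known under any ordering, so the baseline is the one NSI measurement that the design can still keep free of that knowledge.

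**Working it through.** **Order of steps.** Section 10.1 gives: screen, consent, assignment, baseline evaluation, scheduling of treatment. Section 9.5 gives: screening, consent, baseline evaluation. It omits assignment, so it fits either order and does not correct section 10.1. The password protection in section 10.1 governs storage of the list, not the moment of release. "Figure 1. Study Procedure Overview" appears in the text only as a caption, so what it shows is unknown here.

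**The plan's own power figure.** Section 11.5 gives 140 participants, 85% power, two-sided alpha 0.05 and 20% attrition, but no effect size and no SD, so the 85% can only be solved backwards.

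- Analysed per arm: 140 × 0.8 / 2 = 56.
- Two-sample t test with 110 degrees of freedom (noncentral t): 85% power corresponds to a difference of 0.571 SD of change.
- At assumed SDs of 10, 15 or 20 points, that is 5.7, 8.6 or 11.4 NSI points.

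This point does not dispute the power figure; it only supplies the scale.

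**How a shift enters the contrast.** Let knowledge of the arm move reported NSI in one arm, relative to the other, by b points at baseline and by p points after treatment.

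- Unadjusted change: bias in the difference of mean reductions = b − p. If p = b, the bias is zero. If p = 0, the full b enters.
- Baseline as a covariate with slope β: for a baseline-only shift (p = 0), the bias is β × b.

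**Illustration with p = 0.** The standard error of the difference is SD × √(2/56), and the false-positive rate is the two-sided noncentral t rejection probability with noncentrality bias / SE. The covariate column takes β = 0.5 and, for simplicity, keeps the same SDs. The bias is then 0.5 × 2 = 1 point, so it repeats the 1-point column.

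| Assumed SD of change | SE | 1-point shift, unadjusted | 2-point shift, unadjusted | 2-point shift, covariate slope 0.5 |
|---|---|---|---|---|
| 10 | 1.89 | 8.2% | 18.2% | 8.2% |
| 15 | 2.83 | 6.4% | 10.8% | 6.4% |
| 20 | 3.78 | 5.8% | 8.2% | 5.8% |

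Without a shift the rate is 5.0%. For example, with SD 10 and a 2-point shift, 2 / 1.89 = 1.06, which gives 18.2%. The SDs, the shifts and the slope are all assumptions; the protocol gives none of them.

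**The case against.** The evidence for the order is thin. It rests on one sentence in which assignment and evaluation are joined by a plain conjunction. The paragraph is not strictly chronological either, since it speaks of enrolling people before it describes the screen. Section 9.5 fits a baseline-first order at least as well, and the overview figure that might settle the matter is not shown. All of this stands as a limit on what can be claimed. It does not remove the point, because section 10.1 is the only available text that places assignment relative to baseline, and it names assignment first.

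A reader might infer that participants are told their arm before baseline. The documents do not support that. Assignment is not disclosure, and the protocol is silent on when the arm is released. What can be said is that nothing in the available text prevents early disclosure.

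A reader might also infer that any baseline shift passes in full into the primary result. That is true only of an unadjusted change score, and only if the shift is gone after treatment. Section 11.6 names change but no model for this contrast, and the post-treatment NSI is open to the same influence. A shift that persists unchanged cancels in the unadjusted contrast. In that case an arm-naive baseline would not reduce the bias, because the post-treatment shift would remain uncancelled. This objection also stands, and it is why the figures above are an illustration and not an estimate.

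Finally, eligibility requires symptoms that are atypical against norms (sections 9.5 and 12.5), so some symptom score may exist before assignment. It could serve as a check, but section 10.1 assigns the role of baseline to the later evaluation.

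**Conclusion.** The point holds in limited form. Section 10.1, as written, allows the self-reported NSI baseline behind the first primary contrast to be collected with the arm known, and nothing in the available text rules this out. It is not shown that this will happen or that any bias will result; the size and direction of a shift are unknown and may be zero.

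Under the stated assumptions, a 1- or 2-point shift confined to baseline would raise the false-positive rate of an unadjusted change contrast from 5% to between 5.8% and 18.2%. Adjustment for baseline at a slope of 0.5 would hold the 2-point case to between 5.8% and 8.2%. The conclusion depends on one sentence and could change if Figure 1 shows baseline first, although section 10.1 would then need to be brought into line with it. The change is worth making because it closes off a possible bias at almost no cost.

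**What to change.** Reword section 10.1 along these lines: after screening and consent, participants complete the full pre-treatment evaluation, including the NSI; only then is the assignment generated or released to participant and staff, one at a time, by the biostatistician or another existing team member who neither enrols nor assesses participants. Align Figure 1 if it shows the other order.

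The sample size stays at 140, and no visit or measure is added. The cost is that someone in that role must be available to release an assignment after each baseline evaluation. The change protects the baseline only; post-treatment NSI reports will still be made with the arm known.

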11.2 Sample Size – 140 Participants

11.3 Total number of subjects requested (including records and specimens) – 140

11.4 If you are recruiting by study arm, please identify the arms of the study and how many subjects will be enrolled in each arm –

This research project will involve two study arms. Arm 1 participants will receive the SAET intervention. Arm 2 participants will receive the SCG intervention. There will be 70 subjects enrolled in each of the two arms.

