11.5 Please provide a justification for your sample size

With 140 participants, 70 in each intervention arm, we will be able to potentially detect a significant difference in change in neurobehavioral symptoms between the two physical activity interventions (i.e., SAET and SCG) with an 85% power using a two-tailed test and an alpha of 0.05. This estimate is based on similar research on a civilian population (Kaplan, Vasterling, & Vedak, 2010), and takes into consideration a 20% attrition. The 140 participants recruited will suffice to address the research question for secondary aims given the same parameters.

11.6 Data Analysis Plan Complete description: Background, Objectives, Design, Step by Step how the project is going to be done

Primary Aim: Neurobehavioral symptoms: Primary analyses will evaluate whether change in neurobehavioral symptoms from pre- to immediate post-treatment, as well as from immediate post-treatment to 3 months post-treatment, differ between the physical activity interventions. In addition to assessing change in symptoms continuously, we will also evaluate reaching a clinically-relevant change in neurobehavioral symptoms (defined as a change in NSI score of 8 points) (Belanger et al., 2016). Secondary analyses will investigate differences in overall change in neurobehavioral symptoms from pre-treatment to 3 months post-treatment between the interventions using multilevel mixed-effect modeling. This approach will take into consideration between-subject variance based on randomized group, as well as within-subject variance for repeated measures. Analyses will be based on intention to treat (ITT).

Sub-Aim 1: Cognitive Performance: Similar statistical approach as Aim 1 will be conducted for Sub-Aim 1. Exposure will remain as the type of intervention (i.e. SAET vs. SCG); however, outcome will be on global deficit score based on the cognitive test scores.

Sub-Aim 2: Physiological Adaptation: Analysis of Variance (ANOVA) will be utilized to determine differences in continuous variables of physiological adaptation (i.e., cerebrovascular flow, improved cardiovascular health) between interventions.

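### The option to change the allocation ratio mid-recruitment cannot be needed for numbers assigned, is worth at most about 0.6 point of power at the planned attrition, and opens a small avoidable route to period bias

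*Protocol*

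**What the plan says.** Protocol Section 10.1 describes 1:1 randomisation in blocks of 6, kept in force until everyone is assigned, with 70 in each group. Section 11.4 repeats the target: "There will be 70 subjects enrolled in each of the two arms".

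Section 10.1 then adds three sentences that allow the ratio to move. One plans a look at the group sizes at mid-recruitment: "Halfway during recruitment, the sample size will be reassessed for balance between the two groups". Another says what may follow from that look, with an illustrative ratio: "If needed, adjustment of randomization, for example, to a 2:1 ratio, will be conducted but maintaining the block size of 6". The last leaves room for more than one such change: "Periodic adjustment may be necessary to obtain the minimum sample size for this project".

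The protocol gives no imbalance that would trigger the change, no favoured arm and no number for the minimum.

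Section 11.5 claims a detectable difference "with an 85% power using a two-tailed test and an alpha of 0.05" and says that the figure "takes into consideration a 20% attrition". It states no effect size or SD. Of the mixed model, Section 11.6 says: "This approach will take into consideration between-subject variance based on randomized group, as well as within-subject variance for repeated measures". It mentions neither recruitment period nor a changed ratio.

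**The concern.** The clause is offered as a way to keep the groups balanced, but the permuted blocks already do that. If they do, the clause adds nothing for numbers assigned and can serve only to offset unequal dropout.

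A change of ratio part-way through also has a known side effect. The favoured arm draws more of its participants from the later period. If the outcome (here, NSI change) shifts over recruitment, part of that shift enters the arm comparison unless the analysis adjusts for period. The question is whether the power gained could justify that exposure and the departure from 70 per arm.

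**Working it through.** **Inputs.** From the protocol: 1:1, blocks of 6, 70 + 70 (Sections 10.1 and 11.4); 85% power, two-sided 0.05, 20% attrition (Section 11.5); 2:1 as the example ratio (Section 10.1). Assumed, because the protocol does not give them: effect size, attrition by arm, and drift over recruitment.

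**1. The plan's own figure.** 70 × (1 − 0.20) = 56 completers per arm. The 85% power cannot be reproduced independently without an effect size. Solving 85% power at 56 per arm by noncentral t gives d = 0.571, which is used below.

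**2. Numbers assigned under 1:1.** There are 20 orderings of a block of three and three. The largest difference at any moment is 3. At n = 70 (11 full blocks plus 4) the difference is 0 in 12 of 20 orderings and 2 in 8 of 20. At n = 140 (23 blocks plus 2) it is again 0 or 2, so 69/71 at worst. No ratio change can be needed on this ground.

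**3. Securing 56 completers per arm.** Take the unstated minimum to be 56 per arm. With attrition a and b, reaching 56 in both arms within 140 requires 56/(1−a) + 56/(1−b) ≤ 140, that is, 1/(1−a) + 1/(1−b) ≤ 2.5. Under plain 1:1 the variance factor is (1/70)[1/(1−a) + 1/(1−b)]. Under that condition it is at most 2.5/70 = 1/28 = 1/56 + 1/56. So whenever a switch could deliver 56 per arm, plain 1:1 already has the planned precision.

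Example, 25%/10%: 56/0.75 + 56/0.90 = 136.9. Five 2:1 blocks give 75/65 assigned and 56.3/58.5 completers, against 52.5/63.0 under 1:1. Power is 85.8% either way.

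**4. Power under unequal loss, no period term.** Variance factor 1/n₁ + 1/n₂ in completers. A full switch means 35 + 70 × 2/3 = 81.7 against 35 + 70 × 1/3 = 58.3, favouring the arm with the higher loss.

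| Loss | 1:1 | Full second-half 2:1 | Best gain, any switch length |
|---|---|---|---|
| 20%/20% | 85.0% | 84.0% | 0 |
| 30%/10% | 84.5% | 84.2% | 0.13 point |
| 35%/5% | 83.7% | 83.8% | 0.31 point |
| 40%/0% | 82.7% | 83.2% | 0.57 point |

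These rows all average 20% loss. Beyond the plan, the best gain is 0.83 point at 50%/10%, 1.1 at 50%/0% and 1.9 at 60%/0%.

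**5. Power with a factor separating the 1:1 and 2:1 stretches.** The best result over switch lengths is −0.06 point at 40%/0% and −0.04 at 50%/10%, and there is no gain at losses up to 50%/0%. A full switch gives 82.9% at 20%/20% (a loss of 2.1 points), loses 1.7 points at 25%/15%, and gives 83.1% at 30%/10% (a loss of 1.4).

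**6. Period mix if the clause is used.**

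- Full switch: 46.7/81.7 − 23.3/58.3 = 0.571 − 0.400 = 0.171 of any between-half shift enters an unadjusted comparison.
- Five 2:1 blocks: 40/75 − 30/65 = 0.072.

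| Assumed shift | Full switch: bias, type I error | Five blocks: bias, type I error |
|---|---|---|
| 0.25 SD | 0.04 SD, 5.3-5.6% | 0.02 SD, 4.9-5.0% |
| 0.5 SD | 0.09 SD, 6.2-7.2% | 0.04 SD, 4.7-4.9% |
| 1 SD | 0.17 SD, 9-12% | 0.07 SD, 4.0-4.4% |

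Type I error is from simulated pooled t-tests with within-period SD 1. The ranges cover no loss and assumed loss (20% in both arms for the full switch, 25%/10% for five blocks). With a period term it is about 5% throughout.

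**The case against.** The case for leaving the clause alone has real substance.

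- It is conditional, 2:1 is only an example, and its declared purpose is balance. A run to 82/58 fits that purpose poorly unless losses are very unequal. This stands: the full switch is a worst case.
- No document reports any drift, recruitment is at one base, and change scores remove shifts in baseline level alone. This stands too. The shifts above are assumptions, and at 0.25 SD even the full switch barely moves the type I error.
- A period term, trigger and favoured arm could sit in an SAP or randomisation plan that is not shown. So their absence from the protocol is not a defect in itself, and Section 11.6 need not be a complete list of covariates.
- A contingency is meant for extreme losses, where the gain does exceed 1 point. True at 50%/0% and beyond without a period term, but that is far outside the 20% plan, and with a factor for the allocation stretch nothing is gained up to 50%/0%.

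A reader might infer three stronger claims that the protocol does not support. One is that the trial's type I error is inflated to 9-12%: that needs the full switch, a 1 SD shift and no adjustment together. Another is that the switch can never bring both arms to 56 completers: at 25%/10% it does, although 1:1 already holds the power there. The third is that Section 10.1 hides a contradiction: the 70/70 figure is a target with the contingency disclosed beside it, so the conflict arises only if the clause is used.

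**Conclusion.** The point holds as a minor one. The ratio change is unnecessary for numbers assigned; that follows from the block design alone. Its value against unequal loss is at most about 0.6 point of power at the planned 20% overall attrition. It is negative if losses are equal, and it vanishes once the 1:1 and changed-ratio stretches are separated in the model. The power figures rest on d = 0.571, back-solved from 56 completers per arm; letting d run from 0.05 to 1.5 raises the largest gain at planned attrition only to 0.70 point.

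The possible harm is modest and conditional on use at length, drift in the outcome and an analysis without a period term. The clause therefore carries some risk for almost no return, but it does not invalidate the design.

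**What to change.** Delete the reassessment, 2:1 and periodic-adjustment sentences from Section 10.1, keep 1:1 blocks of 6 throughout, and follow all randomised participants under the stated intention-to-treat principle. The cost is an option worth about 0.6 point of power or less at the planned attrition.

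If the clause is kept, state the trigger and the favoured arm. Include allocation period (1:1 stretch versus changed-ratio stretch) as a factor in every between-arm comparison: the mixed model, the ANOVAs and the Poisson regression. Reconcile the 70-per-arm statements in Sections 10.1 and 11.4 with it. That removes the bias route, but a full switch would then lose up to about 2 points of power.
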